5.3. Management of the Investigational Product

5.3.1. Packaging and Labeling

The vial and carton labels will contain the drug name, dosage form, lot number, method of use, storage conditions, shelf life, manufacturer and other information that may be required by the regulatory agency, and indicate “investigational use only” in accordance with regional regulations.

5.3.2. Receipt

Upon receipt of the investigational product, the investigator or designee will verify that an appropriate shipping temperature has been maintained, conduct an inventory count, sign the drug receipt form and send a scanned copy to the sponsor contact as designated on the form. If a temperature excursion occurs, the sponsor should be notified immediately, and the investigational product must be quarantined and maintained under the correct storage conditions until further instructions are provided by the sponsor. The temperature excursion form will need to be completed and returned to the sponsor. The original drug receipt form and packing slip must be retained in the investigator's pharmacy records.

5.3.3. Storage

Records of the actual storage conditions during the period of the study must be maintained (e.g., records of the date and time and the initials of the person performing the check, the temperatures of the

refrigerator used for storage of trial supplies, continuous temperature recordings or regularly maintained temperature alarm systems used in conjunction with temperature recording). If a temperature excursion occurs, the sponsor should be notified immediately, and the investigational product must be quarantined and maintained under the correct storage conditions until further instructions are provided by the sponsor.

5.4. Accountability and Destruction

The investigator or designee(s) must maintain an inventory record of the investigational product received, dispensed, administered, and returned. The investigator or designee(s) should record the dispensing of the study drug to individual subjects and disposition of any remaining study drug after dosing in the investigational product accountability record. Investigational product accountability records and temperature monitoring logs must be made available to the sponsor or designated monitoring personnel for the purpose of conducting drug accountability.

All unused medication is not to be stored or subsequently used and will need to be properly disposed of in accordance with the institutional policy and procedure, and disposition must be recorded on the investigational product accountability record.

The sponsor or designee will provide guidance on the destruction of unused investigational product. If destruction is authorized to take place at the investigator site, the investigator must ensure that the materials are destroyed in compliance with applicable environmental regulations, institutional policy, and any special instructions provided by SCT, and all destruction must be adequately documented.

5.5. Return of Drugs

A representative from the sponsor or designee will inspect the study drug inventory, perform accountability, and will arrange for the disposition of any remaining unused study drug. No study drug may be returned to the sponsor designee without the representative from the sponsor or designated personnel first inspecting the study drug inventory and accountability documentation.

5.6. Randomization and Blinding

Each subject will be assigned a unique identification number. The subject identification (SID) number will be used to identify the subject throughout the study and will be entered on all study documentation. The SID will be an 8-digit number with the first 4 digits corresponding to the site number and the last 4 digits sequentially assigned by the site at screening. If a subject discontinues from the study at any time, his/her study number cannot be reassigned to another subject.

Phase II part of the study: Patients will be randomly assigned to receive SCTA01 (15 mg/kg), SCTA01 (50 mg/kg) or placebo a 1:1:1 ratio. The randomization schedule will be stratified by country.

Phase III part of the study: Patients will be randomly assigned to receive SCTA01 (X mg/kg or X mg) or placebo in a 1:1 ratio. The randomization schedule will be stratified by country.

An interactive web response system (IWRS) will be used to administer the randomization schedule. An independent CRO statistician will generate a permuted block randomization schedule for IWRS, which will link the sequential patient randomization numbers to the treatment codes.

Each patient will be assigned a randomization number which is different from the patient identification number. Once a randomization number has been allocated to a patient, it cannot be assigned to another patient.

To ensure the treatment assignment is unbiased and concealed from all individuals involved in the study, all enrolled patients are randomized to SCTA01 or placebo group using the following procedures: 1) randomization data are kept strictly confidential until the time of final analyses, and will not be accessible to anyone involved in the conduct of the study with the exception of the IDMC team and unblinded statistician; 2) the identity of the treatments will be concealed by the use of study drugs (SCTA01 and Matching Placebo) that are all identical in packaging, labeling, schedule of administration and appearance.

5.7. Other Considerations

The investigator should administer the investigational drug or placebo to the subjects according to the protocol. Medication errors should be reported to the sponsor/CRO immediately as a protocol deviation. Medication errors can cause AE/SAE or clinical abnormal results.

6. STUDY INTERVENTION DISCONTINUATION

6.1. Individual Infusion Halting

In rare instances, it may be necessary for a subject to permanently discontinue study intervention. If study intervention is definitively discontinued, the participant will remain in the study for follow-up.

For an individual subject, the infusion must be terminated and not restarted if severe infusion-related reaction(s) mentioned in Section 3.5 occur.

The treatment for any given subject may be stopped for SUSARs related to SCTA01, clinically significant adverse reactions, severe laboratory abnormalities, or any other medical conditions that indicate to the investigator that continued dosing is not in the best interest of the patient.

In addition, a subject in this clinical study may discontinue study drug at their requests for any reason. After the discontinuation, every effort should be made to encourage the subject to remain in the study for the duration of their planned outcome assessments.

The reason for subject discontinuation of study drug should be documented in the case report form.

6.2. Study Halting

Given the potential severity of COVID-19, there are no pre-specified study stopping rules. Instead there will be close oversight by the project team and frequent IDMC reviews of the safety data.

The clinical trial should be terminated if there are any of the following situations:

- The sponsor finds that SCTA01 has potential safety hazards or the research has quality problems and requires the trial to be terminated completely;
- The IDMC evaluates the clinical trial results and believes there is a potentially significant safety risk;
- The relevant government authorities request the termination of the trial.

6.3. Withdrawal from the Study

Subjects are free to withdraw from participation in the study at any time upon request, without any consequence. Subjects should be listed as having withdrawn consent only when they no longer wish to participate in the study and no longer authorize the Investigators to make efforts to continue obtaining their outcome data. Subjects who withdraw from this study or are lost to follow-up after signing the informed consent form (ICF) and administration of the study product, will not be replaced. The reason for subject withdrawal from the study will be recorded on the appropriate CRF.

6.4. Lost to Follow-Up

A subject will be considered lost to follow-up if he or she fails to complete all follow-up assessments. In such cases, attempts to contact the subject should be made and these efforts should be documented in the subject's records.

Patients transmitted to comfort care are not considered lost to follow up, but the outcome of the patient should be collected.

7. STUDY PROCEDURES AND EVALUATIONS

All required study procedures and evaluations are to be conducted as outlined in this protocol. In the event of a deviation from the protocol due to an emergency, accident, or mistake, the investigator or designee must notify the sponsor as soon as possible.

Additional assessments (vital signs, ECG, laboratory test, etc.) can be done at the discretion of the investigators as clinically indicated.

7.1. Time and Events Schedule

The schedule of study assessments is provided in Tables 2, 3, and 4 below. Flexibility is allowed in scheduling the visits according to visit time windows as specified in table below.

For a procedure required at early withdraw (Table 4), it does not need to be performed if the procedure is not a daily required procedure and it has been done in 3 days before subject's withdraw.

Table 2. Schedule for Screening Visit

Study Process	Screening Period	Comments
Visit	V1	
Visit day	D-3~ D-1	
Informed consent	X	
Demographics	X	Including birth date, sex, race, and ethnicity.
Medical history	X	Medical history prior to signing the ICF including: - The day of onset of COVID-19 signs and symptoms. - History of medication allergies. - History of medical conditions within 30 days prior to signing the ICF including but not limited to chronic oxygen requirement prior to onset of COVID-19. - Ask if they are participating in another clinical trial or plan to enroll in another clinical trial in the next 30 days.
Physical examination	X	Testing items see Section 7.2; Physical examination is focused on lung auscultation.
β-HCG	X	For non-postmenopausal female subjects or who have not undergone surgical sterilization
Serum chemistry	X	Testing items see Section 7.2.
SARS-CoV-2 infection confirmation	X	Has documented laboratory-confirmed SARS-CoV-2 infection as determined by PCR. Note: Patient can be enrolled before SARS-CoV-2 infection has been confirmed and can be tested by any approved clinical test other than PCR as long as SARS-CoV-2 infection is then confirmed by PCR.
Vital signs	X	Include body temperature, pulse rate, blood pressure, respiratory rate in semi-supine position
Diagnosis of severe COVID-19 infection	X	Use one of following criteria: 1) respiratory rate; 2) SpO ₂ ; 3) PaO ₂ /FiO ₂ or SpO ₂ /FiO ₂ ; 4) chest X-ray or CT. Refer to Section 4.1 for details.
8-Point Ordinal Scale	X	
Inclusion/Exclusion criteria review	X	
AEs	X	Record the AEs from after obtaining the Informed Consent
Prior treatments within the last 30 days	X	

Table 3. Schedule for Treatment Visit

Study Process	Treatment Period	Comments
Visit	V2	
Visit day	D1	
Randomization	X	
Height	X	
Weight	X	
Vital signs	X	Refer to Section 7.2.2. At 15 ± 5 , 30 ± 5 , 45 ± 5 , 60 ± 5 , 90 ± 10 , 120 ± 10 , 150 ± 10 , 180 ± 10 , 240 ± 10 , 300 ± 10 minutes after the beginning of infusion (i.e. every 15 ± 5 minutes for the first hour of infusion, every 30 ± 10 minutes until the end of infusion and every 60 ± 10 minutes for 2 hours after the end of infusion).
Targeted physical examination		Are performed only when needed to evaluate possible adverse events.
12-lead ECG	X	Refer to Section 7.2.3 Test within 2 h (± 10 min) before infusion, and within 2 h (± 10 min) after the end of infusion. Additional ECG examination is at the discretion of the Investigator per standard clinical practice or as clinically indicated.
Hematology	X	Testing items see Section 7.2.5. Sample will be collected before infusion.
Serum chemistry	X	
Urinalysis	X	
Coagulation test	X	
IL-6	X	
Ferritin	X	
Procalcitonin	X	
Thrombin time	X	
D-dimer	X	
Serological samples for anti-spike protein antibodies	X	Blood samples will be collected within 0.5 h (± 5 min) before infusion.
Immunogenicity (ADA) blood samples	X	
PK samples	X	Intensive sampling of Phase II part: - Within 0.5 h (± 5 min) before the beginning of infusion; 1 h (± 10 min) post end of infusion .
Blood for PCR SARS-CoV-2 test	X	Sample will be collected before infusion.

NP or OP swab for SARS-CoV-2 test	X	Sample will be collected before infusion. NP swab preferred. If NP swab cannot be obtained, OP swab may be used.
SpO ₂	X	Record SpO ₂ before infusion, and 1 h (\pm 0 min), 2 h (\pm 0 min), 3 h (\pm 0 min) after the end of infusion. Also record oxygen supplementation: low flow oxygen, high flow oxygen, or other.
8-Point Ordinal Scale	X	To evaluate within 30 ~ 60 min before infusion.
Administration of SCTA01/Placebo	X	The dose should be given within 24 hours after randomization.
AEs	X	
Concomitant medications	X	Items see Section 3.6.1.

Table 4. Schedule for Follow-up Visit

Study Process	Follow-up Period										Comments
	V3	V4	V5	V6	V7	V8	V9	V10	V11	V12	
Visit											
Visit day	D2	D3	D5	D8	D11	D15	D22	D29	D60	D120	
Window period (\pm day)	\pm 0 d	\pm 0 d	\pm 1 d	\pm 1 d	\pm 1 d	\pm 2 d	\pm 3 d	\pm 3 d	\pm 3 d	\pm 7 d	Early Withdraw
Vital signs		Daily until discharge									
Targeted physical examination		Performed only when needed to evaluate possible adverse events									
β -HCG	Only when potential pregnancy is suspected and at the end of the study								X		
12-lead ECG		X		X		X		X		X	
Hematology		X		X		X		X		X	
Urinalysis		X		X		X		X		X	
Serum chemistry		X		X		X		X		X	
Coagulation test		X		X		X		X		X	
IL-6		X		X		X		X		X	
Ferritin		X		X		X		X		X	
Procalcitonin		X		X		X		X		X	
Thrombin time		X		X		X		X		X	
D-dimer		X		X		X		X		X	
Immunogenicity blood samples							X		X	X	

PK samples				X ^{1,2}	X ¹	X ^{1,2}			X ^{1,2}		1: Intensive sampling of Phase II part: Blood samples will be collected in the same 30 subjects as the Table 3. 2. Sparse sampling of Phase II part: Blood samples will be collected in the remaining subjects (excluding the 30 subjects with intensive PK sampling) of each group of Phase II part.
Blood for SARS-CoV-2 test	X		X		X	X		X	X		Only performed while patient is in hospital or attends an in-person visit.
NP or OP swab for SARS-CoV-2 test	X	X	X	X	X	X		X	X		Continue testing at the scheduled time-point while hospitalized or attends an in-person visit, until the NP or OP swab samples viral RNA test is negative. NP swab preferred. If NP swab can't be obtained, OP swab may be used.
Sequencing the gene encoding spike protein		Will be tested in subjects who do not achieve a reduction in viral shedding or persistence viral presence or have a rebound in viral shedding following suppression									Using reserved NP or OP swab samples. No additional sampling is required.
8-Point Ordinal Scale	Daily until discharge			X	X	X			X		Only performed while patient is in hospital or attends an in-person visit, otherwise performed by phone call to assess clinical status (ordinal scale). The date and cause of discharge or re-hospitalization after discharge should be recorded.

Concomitant medications		Daily until discharge	
SpO ₂		Daily until discharge	Report the best reading if multiple readings are obtained in a day. Also record oxygen supplementation: low flow oxygen, high flow oxygen, or other.
AEs		Daily until discharge and biweekly via phone call after discharge until 120 days.	
ADE		Monitor for new infections and adverse events until 120 days (if discharged, via biweekly telephone call, in-person or virtual visit).	

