5.2. Administration

Each participant will receive a single intravenous infusion of either SCTA01 or placebo. Infusion volume will be 500 mL and infusion time is 3 hours (\pm 0 minutes).

Phase II part of the study: Subjects will receive a single dose of SCTA01 (15 mg/kg), SCTA01 (50 mg/kg), or placebo within 24 hours after randomization.

Phase III part of the study: Subjects will receive a single dose of SCTA01 (X mg/kg or X mg) or placebo within 24 hours after randomization.

Further instruction on the preparation and administration of the investigational product will be provided to the site in Pharmacy Manual.

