7.2.5. Clinical Safety Laboratory Assessments

Fasting is not required before collection of laboratory samples; Day 1 clinical laboratory tests are performed prior to infusion as a baseline.

Blood will be collected at the time points indicated in the Tables 2 to 4. Testing items including:

- Hematology: Red blood cell count; hemoglobin concentration; platelet count; white blood cell count; absolute value and percentage of: lymphocytes, monocytes, neutrophils, eosinophils, basophils;
- Urinalysis: Urine occult blood, urine bilirubin, urobilinogen, urine ketone body, urine protein, urine nitrite, urine glucose, urine pH, urine specific gravity, urine white blood cells, urine white blood cells (high power field), urine red blood cells, and urine red blood cells (high power field);
- Serum chemistry: AST, ALT, total bilirubin, direct bilirubin, indirect bilirubin, total protein, alkaline phosphatase, glutamyl transpeptidase, urea, blood creatinine, albumin, creatine kinase, C-reactive protein, blood glucose, potassium, and sodium, chlorine, lactate dehydrogenase (LDH);
- Coagulation test: Prothrombin time, activated partial thromboplastin time, fibrinogen;
- IL-6; Ferritin; Procalcitonin; Thrombin time; D-dimer.

The investigator must review the laboratory report, document this review, and record any clinically relevant changes occurring during the study in the AE section of the CRF. Clinically significant abnormal laboratory findings are those which are not associated with the underlying disease, unless judged by the investigator to be more severe than expected for the participant's condition.

All laboratory tests with values considered clinically significantly abnormal during participation in the study should be repeated until the values return to normal or baseline or are no longer considered clinically significant by the investigator or medical monitor.

If such values do not return to normal/baseline within a period of time judged reasonable by the investigator, the etiology should be identified and the sponsor notified.

All protocol required laboratory assessments must be conducted in accordance with the laboratory manual.

If laboratory values from non-protocol specified laboratory assessments performed at the institution's local laboratory require a change in participant management or are considered

clinically significant by the investigator (e.g., SAE or AE or dose modification), then the results must be recorded in the CRF.

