9.6. Safety Analysis

The general safety summaries will include treatment group and placebo group, comprising all patients in the safety set.

Adverse events will be tabulated by treatment group. The number and percentage of patients with at least one AE will be presented along with a breakdown by system organ class (SOC) and Preferred Term (PT), with each patient being counted once at each summarization level. This summary will be repeated for treatment-related AEs, AEs that lead to study drug discontinuation, by relationship to study drug, by intensity and for SAEs.

Laboratory test results, vital signs data, and ECG data will be presented in tables summarizing absolute values and change from baseline by treatment group, with shift tables included as appropriate.

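### No Day 1 vital signs are scheduled before the infusion starts, and the baseline for their planned change-from-baseline tables is undefined

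*Combined protocol and SAP*

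**What the plan says.** **Day 1 schedule.** The vital-signs row of Table 3 (section 7.1) lists readings at 15, 30, 45, 60, 90, 120, 150, 180, 240 and 300 "minutes after the beginning of infusion". Its explanatory text restates the same pattern, ending with readings "every 60 ± 10 minutes for 2 hours after the end of infusion". Section 5.2 gives the infusion length: "Infusion volume will be 500 mL and infusion time is 3 hours". Section 7.2.2 refers back to Tables 2 to 4 for timing and leaves extra readings to clinical indication or the investigator's judgement.

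**Earlier readings.** The only other vital signs scheduled before dosing are at screening, Day -3 to Day -1. Table 2 describes them: "Include body temperature, pulse rate, blood pressure, respiratory rate in semi-supine position". Table 3 adds a dosing allowance: "The dose should be given within 24 hours after randomization".

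**Other Day 1 measurements.** In the same table, laboratory samples, serology, PCR samples, SpO2 and the ordinal scale all have a time before infusion. The ECG is taken both "before infusion, and within 2 h" after the infusion ends.

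**Analysis.** Section 9.6 states: "Laboratory test results, vital signs data, and ECG data will be presented in tables summarizing absolute values and change from baseline by treatment group". The synopsis says the same in substance. For laboratory tests, section 7.2.5 fixes the reference: "Day 1 clinical laboratory tests are performed prior to infusion as a baseline". There is no matching sentence for vital signs.

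**The concern.** A change-from-baseline table needs a baseline that is both defined and measured. For vital signs the protocol supplies neither on the day of dosing. These are acutely ill inpatients, in whom temperature, blood pressure and respiratory rate can move over a few days without any drug effect. A change measured from an older value therefore carries disease course and the effect of supportive care as well as anything the infusion does.

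The omission looks unintended. Serum chemistry and the ordinal scale are recorded at screening and again on Day 1 before infusion, so for those measures the plan does not rely on the screening value. Section 2.8 also shows the use of a pre-dose value: a fall in tidal volume in monkeys was judged unrelated to the test article partly because it was seen before dosing.

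Two things are at stake. One is the precision of the vital-sign change tables. The other is the ability to judge whether an abnormal value early in the infusion was already there. Section 3.5 lists hypotension among the infusion signs without a numeric threshold, and section 3.4 lets the frequency of infusion reactions influence whether premedication is adopted.

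**Working it through.** The plan states no figure on this point, so there is nothing to reproduce. The check has three parts.

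**1. Does any Day 1 window reach back before the infusion?**
Inputs: the ten times and their tolerances (Table 3), and a 180-minute infusion (section 5.2).
- Verbal rule for 180 minutes: 15, 30, 45, 60; then 90, 120, 150, 180; then 180 + 60 = 240 and 180 + 120 = 300. This matches the listed times exactly, so the list has not lost an entry.
- Window for the first reading: 15 ± 5, that is 10 to 20 minutes after the start. The earliest permitted reading is 10 minutes in.
- Share of the infusion given by the first reading, if the rate is constant (assumption): 15/180 = 8%, with a range of 10/180 = 6% to 20/180 = 11%.

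**2. How old is the screening value at infusion?**
Inputs: screening Day -3 to Day -1 (Table 2), dosing up to 24 hours after randomisation on Day 1 (Table 3). No Day 0 is assumed.
- Shortest: Day -1 to Day 1 is one calendar day. An evening screening followed by a morning infusion is under 24 hours.
- Longest: Day -3 to Day 1 is 3 days; 3 + 1 = 4 days with the full dosing allowance.
- If the numbering did include a Day 0, the longest gap would be 4 + 1 = 5 days.

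The protocol gives no typical gap.

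**3. How much noise could this add?**
All inputs here are assumptions, because the protocol gives no SD or correlation for vital signs. Take systolic pressure with SD σ at both times and correlation ρ between the baseline and the on-infusion reading.
- SD of change = σ√(2(1 − ρ)).
- Probability of an apparent fall of 20 mmHg or more at one reading, with no true mean change = Φ(−20 / SD of change).

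| Baseline | σ | ρ | SD of change (mmHg) | P(fall ≥ 20) |
|---|---|---|---|---|
| Just before infusion | 15 | 0.8 | 15√0.4 = 9.5 | Φ(−2.11) = 1.8% |
| Screening | 15 | 0.4 | 15√1.2 = 16.4 | Φ(−1.22) = 11.2% |
| Screening, closer correlation | 15 | 0.6 | 15√0.8 = 13.4 | Φ(−1.49) = 6.8% |

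- Variance ratio: (1 − 0.4)/(1 − 0.8) = 3. With ρ = 0.6 at screening it is 0.4/0.2 = 2. If the immediate reading correlated only 0.7, with 0.6 at screening, it would be 0.4/0.3 = 1.3.
- For σ from 12 to 20, the share with an apparent fall goes from 0.4–5.7% (ρ = 0.8) to 6.4–18.1% (ρ = 0.4).

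The direction needs only that an older reading correlates less with the on-infusion reading than an immediate one does. The 20 mmHg cut-off is illustrative; the protocol plans no such outcome.

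**The case against.** The other side has several good points, and most of them limit the finding without removing it.

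- **Baseline is undefined; it is not stated to be screening.** A reader might infer that the plan adopts a stale screening value. The protocol does not say so, and sections 9.7.1 and 9.9 leave some analysis detail to a SAP. This stands. However, a later definition cannot supply a reading that was never scheduled. An unscheduled reading is allowed but not required, so it would be available for some patients and sites and not others.
- **Heart rate is covered.** A reader might infer that tachycardia cannot be judged. The pre-infusion ECG is required, and section 7.2.3 specifies a machine that calculates heart rate. This stands. Pre-infusion SpO2 and the ordinal scale also describe respiratory status, but they do not replace blood pressure, temperature or respiratory rate.
- **The on-infusion series is dense.** A reader might infer that no fall during infusion can be told from drift since screening. A fall after the first reading shows within the series itself. Only a change already present at that first reading lacks a near-infusion reference. Using the first reading as baseline would not help, because exposure has begun by then.
- **Events of special interest are graded otherwise.** A reader might infer that infusion reactions would be missed or misgraded. Table 6 (section 8.2.7) grades them on signs, symptoms and intervention, not on change from baseline, so the documents do not support that.
- **The consequence is limited.** Vital signs are not among the safety endpoints listed in section 1.5, absolute values are tabulated as well, and the placebo arm has the same schedule. All of this stands.

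**Conclusion.** The concern holds in a limited form. Following the schedule exactly yields no blood pressure, temperature or respiratory rate between screening and at least 10 minutes into the infusion, and the baseline for the planned change tables is not defined. A reader might infer bias between the arms. There is none from this source, because allocation is randomised and blinded and all arms share the schedule. The cost is lower precision in the change tables and weaker patient-level attribution of a change seen at the first on-infusion reading.

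The size of the loss cannot be fixed from the documents. Under the assumptions shown, the variance of the change rises by a factor between about 1.3 and 3. The primary endpoint, the dose-selection rule and the error control are unaffected. This is a worthwhile, inexpensive improvement to safety data collection, not a threat to the trial's conclusions.

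**What to change.** 1. In Table 3, add one Day 1 vital-sign set before the infusion starts, for example alongside the pre-infusion SpO2 reading. Alternatively, record the last ward set taken before the infusion, with its time.
2. In section 9.6 (and the SAP), define the vital-sign baseline as the last value before the start of infusion, in line with what section 7.2.5 already does for laboratory tests.

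Both are needed: the definition alone would fall back on screening wherever no later reading was recorded. The cost is one bedside reading or one transcription in inpatients who already have ten sets that day, plus one line in Table 3 and one in section 9.6. It changes no dose, infusion rule or stopping rule.
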